2.1.2. Endpoints

Primary Endpoint

The primary endpoint is RSV viral load (measured by qRT-PCR in the mid-turbinate nasal swab specimens) AUC from immediately prior to first dose of study drug (baseline) until Day 7.

Secondary Endpoints

The secondary endpoints are:

- Safety/tolerability including AEs, physical examinations, vital signs/peripheral capillary oxygen saturation (SpO₂), ECGs, and clinical laboratory results.
- PK parameters of JNJ-63549109.
- RSV clinical course endpoints:
 - Length of hospital stay from admission to discharge and to readiness for discharge and from study treatment initiation to discharge and to readiness for discharge, with readiness for discharge evaluated by the investigator.
 - Requirement for and duration of intensive care unit (ICU) stay.
 - Requirement for and duration of oxygen supplementation/noninvasive mechanical ventilation support (eg, nasal cannula, face mask, continuous positive airway pressure) and/or invasive mechanical ventilation support (eg, endotracheal-mechanical ventilation or mechanical ventilation via tracheostomy) above pre-RSV infection status.
 - Time to no longer requiring supplemental oxygen above pre-RSV infection status.
 - Time to clinical stability defined as the time from initiation of study treatment until the time at which the following criteria are met: return to pre-RSV infection status (hereafter referred to as “normalization”) of blood oxygen level (ie, without additional requirement of supplemental oxygen compared with pre-RSV infection status), normalization of oral feeding, normalization of respiratory rate, and normalization of heart rate.
 - Time from initiation of study treatment until SpO₂ ≥93% on room air among subjects who were not on supplemental oxygen prior to the onset of respiratory symptoms.
 - Time to respiratory rate, SpO₂, and body temperature return to pre-RSV infection status.
 - Incidence of acute otitis media (defined by the investigator).
- The duration and severity of signs and symptoms of RSV infection as assessed by the PRESORS questionnaire completed by the clinician in the eCOA device.
- RSV viral load as measured by qRT-PCR in the mid-turbinate nasal swab specimens, which will be used to determine the following:
 - RSV viral load over time.

- Peak viral load, time to peak viral load, rate of decline of viral load, and time to RSV RNA being undetectable.
- Proportion of subjects with undetectable RSV viral load at each timepoint.

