9. STUDY EVALUATIONS

9.1. Study Procedures

9.1.1. Overview

The [Time and Events Schedules](#) summarize the frequency and timing of efficacy, PK, biomarker, medical resource utilization, health economic, and safety measurements applicable to this study. There are 2 [Time and Events Schedules](#): 1 schedule for subjects who are hospitalized (up to their hospital discharge); 1 schedule for subjects after they are discharged from the hospital. Repeat or unscheduled samples may be taken for safety reasons or for technical issues with the samples.

The eCOA device will be provided to the parent(s)/caregiver(s) at screening to record the parent(s)/caregiver(s) ratings of the severity of the subject's symptoms (PRESORS) (see [Attachment 5](#)). The parent(s)/caregiver(s) will complete the eCOA twice daily (in the morning and in the evening); after Day 14, eCOA will be completed once daily in the evening (at approximately the same time each day) until the end of the study for subjects who have been discharged from the hospital. Whenever possible, the same parent(s)/caregiver(s) should

complete the eCOA throughout the study. The first parent/caregiver assessment on Day 1 needs to be recorded predose, before the LD. If the screening assessment was performed less than 8 hours prior to the LD, the predose assessment does not need to be performed. The first postdose parent/caregiver assessment must be performed between 6 and 12 hours after the LD (on Day 1 or Day 2, depending on the time of LD).

The investigator/study-site personnel will provide sufficient information to enable the parent(s)/caregiver(s) to complete the parent(s)/caregiver(s) eCOA and will ensure that the eCOA is completed correctly and on schedule to avoid missing or incorrect data.

Prior to completing the screening assessment, the parent(s)/caregiver(s) must complete a training module (included as part of the eCOA device) on how to enter responses to questions in the eCOA device. Study-site personnel will review the completion of the parent(s)/caregiver(s) eCOA on a daily basis.

The clinician eCOA ([Attachment 5](#)) will be completed by the investigator twice daily for the entire duration of hospitalization and once daily at the Day 7, Day 10, Day 14, and Day 28 visits during outpatient follow-up.

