- Floppy/lethargic/poor interaction
- Only responds to pain/unresponsive

7. Signs of increased work of breathing now

7.1. Does the subject show any of these signs of increased work of breathing now? (note all that apply)

- Subcostal retractions
- Intercostal retractions
- Tracheosternal retractions
- Tachypnea [*tachypnea needs defined within the system WHO values pop-up?*]
- None of the above [*cannot be checked if any other options selected*]

7.2. Does the subject show any of these signs of increased work of breathing now? (note all that apply)

- Nasal flaring
- Head bobbing
- Grunting
- Other signs of increased work of breathing not already reported
- None of the above [*cannot be checked if any other options selected*]

8. Does the subject show any signs of cyanosis?

- Yes
- No

9. Describe the subject's coughing now (select one)

- Little or no coughing
- Occasional strong cough, sometimes productive
- Frequent cough, sometimes causing choking, gagging, or vomiting

10. Describe the subject's nasal secretions now (select one)

- None
- Minimal, easily cleared with suctioning
- Moderate, but could be cleared with suctioning
- Extensive, requires frequent suctioning

11. Describe the subject's wheezing now (select one)

- No wheezing
- Terminal expiratory wheezing or only with stethoscope
- Entire expiration or audible during expiration without stethoscope
- Inspiration and expiration without stethoscope

12. Does the subject appear to be dehydrated now?

- Yes
- No

13. Do you have any concerns relating to the subject's overall condition? (select one)

- No concerns (condition is stable or improving)
- Some concerns (may become unstable/requires close observation)
- Extremely concerned (unstable, requires immediate medical review)

14. Overall, how would you rate the subject's current health status? (select one)

- Excellent
- Good
- Fair
- Poor

During hospitalization only:

15. Based on the clinical status of the subject, is the subject ready to be discharged?

- Yes
- No

At the Day 7 visit only (only for studies in which study drug is administered):

16. In general, was the oral dosing of the study medication well tolerated by the subject?

- Yes
- No

17. Study drug administration

17.1 During study drug administration, were any of the following reported? (note all that apply)

- Disgusted expressions after tasting medicine
- Cried after tasting medicine
- Refused (would not open mouth or turned head away to avoid medicine)

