5.3.1.3. RSV clinical outcome

Measurement	Formula
Length of hospital stay (hours) [Time-to event]	
The time from treatment initiation to hospital discharge (=event) in hours.
 
Subjects who complete or withdraw from the study prior to the event will be censored at the date of completion or withdrawal. If the time is not available they will be censored at 12:00. In case of death the subject will be censored at the maximum observed number of hours until the occurrence of the event or censoring for all subjects achieving the event or being censored because of study completion or withdrawal.
 
(Date and time of event or censoring - date and time of first dose of study drug)/3600, rounded to one decimal.

Time to readiness for discharge (hours) [Time-to event]	
The time from study treatment initiation to readiness for discharge (= event) in hours, with readiness for discharge defined by the investigator.
 
Derivation similar as “Length of hospital stay”

Length of hospital stay since hospital admission (hours) [Time-to event]	
The time from hospital admission to hospital discharge (= event) in hours.
 
Derivation of censoring similar as “Length of hospital stay”.
 
(Date and time of event or censoring - date and time of hospital admission)/3600, rounded to one decimal

Measurement	Formula
Time to readiness for discharge since hospital admission (hours) [Time-to event]	
The time from hospital admission to readiness for discharge (= event) in hours, with readiness for discharge defined by the investigator.
 
Derivation similar as “Length of hospital stay since hospital admission”

Duration of intensive care unit (ICU) stay (hours) [Duration]	
The total number of hours a subject stayed in ICU (= event) from first intake until study termination, calculated as sum of [(end date and time of event - start date and time of event)/3600], rounded to one decimal for all separate events per subject
 
If the initial start time is prior to the first dose of study drug, the duration prior to the first dose of study drug will be deducted from the overall duration.
 
If the end date is missing, the end date is considered to be after study completion or withdrawal. If the end date and time is after the study completion/discontinuation, the duration after the date and time of study completion/discontinuation will be deducted from the overall duration. If the time is not available it will be put at 12:00.

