Additionally these time-to event parameters will be analyzed for all ITT-i subjects using Kaplan-Meier analysis as indicated above and using a stratified Gehan test to compare between treatment groups

Time to clinical stability and Time to return to pre-RSV disease level

These time-to event parameters will be analyzed as indicated above using Kaplan-Meier analysis.

The differences in time of active dose regimens versus placebo treatment will be estimated using a Cox proportional hazard model; as baseline covariates, stratification factors, absence/presence of other viral or bacterial infections, and baseline log₁₀ viral load will be added. Treatment effect versus placebo will be reported, including 95% confidence intervals. A Log-log plot of survival will be added to check the proportional hazard assumption.

Additionally, the time-to event data will be analyzed using the logrank test and Gehan-Wilcoxon method.

Incidence of acute otitis media and all-cause mortality

The incidence of acute otitis media and of all-cause mortality will be analyzed similarly. Note that these incidences are only analyzed if any subjects have acute otitis media or if any deaths occur.

The proportion of subjects with presence/absence of acute otitis media and who died yes/no will be shown in a frequency tabulation (with corresponding 95% CI) and per treatment group.

A stratified logistic regression model will be used to analyze the outcome.

Relationship between RSV RNA viral load and clinical outcome

The following relationships will be investigated:

RSV RNA log₁₀ viral load AUC_{0-144h} versus

- Requirement for oxygen supplementation
- Time to end of Oxygen supplementation

- Length of hospital stay
- Time to readiness for discharge
- Length of hospital stay since hospital admission
- Time to readiness for discharge since hospital admission
- Time to clinical stability
- Time to return to pre-RSV functional status

The definitions of these parameters can be found in sections [5.3.1](#).

A Tabulation of the requirement for oxygen supplementation will be presented by quartiles of viral load AUC_{0-144h} .

Kaplan-Meier analysis by quartiles of viral load AUC_{0-144h} will be done for the time to variables.

Relationship between RSV RNA viral load and signs and symptoms of RSV infection

The following relationships will be investigated:

Quartiles of viral load AUC_{0-144h} versus

- Severity of signs and symptoms of RSV infection as rated by the clinician.

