5.4.2. Analysis Methods

Frequency tabulations of each of the individual items at baseline, day 7, 14 and 28.

Severity and Improvement of Signs and Symptoms of the RSV infection

Actual values and changes from baseline will be summarized by treatment group at each scheduled time point for the PRESORS scores (severity), child's temperature, breaths per minute, time spent with the child and hours missed from usual activities.

Mean \pm SE graphs over time for the actual values and changes from reference will be presented.

Analyses of the PRESORS scores may be performed to further investigate validity of this instrument. These will be described outside this SAP and, if performed, will be reported outside the CSR.

Duration of Signs and Symptoms of the RSV infection

See secondary endpoint: Time to readiness for discharge.

Relationship between viral load and duration of signs and symptoms of RSV symptoms as assessed by the PRESORS questionnaire completed by the clinician

Kaplan-Meier analysis by quartiles of viral load AUC_{0-7 days} for the duration of signs and symptoms of RSV symptoms

A summary table including number of subjects included in the analysis, number of subjects censored, 25th and 75th percentiles and median with 95% confidence intervals based on log-log transformation method, will be presented by quartiles of viral load AUC_{0-7 days} parameter.

The relationship between the clinician eCOA and parent(s)/caregiver(s) eCOA responses

The relationship between the severity of signs and symptoms as assessed by the clinician and the parent(s)/caregiver(s) will be assessed using spearman rank correlation between the clinician's score (both during the past 12 hours and now) and the parent(s)/caregiver(s) score. This correlation will be evaluated at baseline and on all scheduled assessments where both the clinician eCOA and caregiver eCOA have been performed. Other methods may be considered as appropriate.

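### The SAP reports symptom duration only as time to readiness for discharge, so the duration half of the PRESORS endpoints contains no symptom resolution

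*SAP*

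**What the plan says.** Protocol 2.1.2 has a secondary endpoint, rated by the clinician on PRESORS, that covers both how long RSV signs and symptoms last and how severe they are. The caregiver-rated counterpart is exploratory. The same section lists time to readiness for discharge separately, among the clinical-course endpoints.

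SAP 5.4.2 handles severity with PRESORS scores and changes by treatment group at each scheduled time point. Under the heading "Duration of Signs and Symptoms of the RSV infection" it has a single line: "See secondary endpoint: Time to readiness for discharge". SAP 5.3.1.3 defines that variable as: "The time from study treatment initiation to readiness for discharge (= event) in hours, with readiness for discharge defined by the investigator".

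The readiness question in the clinician form (Protocol Attachment 5, item 15) reads "Based on the clinical status of the subject, is the subject ready to be discharged" and sits under the instruction "During hospitalization only". Protocol 9.1.1 has the clinician form completed "twice daily for the entire duration of hospitalization and once daily at the Day 7" visit, with three later follow-up visits ending on Day 28.

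SAP 5.3.2.3 also lists "Time to return to pre-RSV functional status" among the outcomes to be related to viral load and refers to 5.3.1 for its definition.

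**The concern.** Readiness for discharge and the end of symptoms are different events. A child can be fit to go home while cough, wheeze or reduced feeding persists, and nothing after discharge can change the readiness time. Under the SAP as written, one discharge variable is reported under two secondary endpoints, and the duration half of the PRESORS endpoint has no measure of its own. The exploratory caregiver duration endpoint has no derivation either. The Kaplan-Meier analysis of symptom duration by viral-load quartile in SAP 5.4.2 has only the same substitute to draw on.

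At stake is what a reader of the report would take a duration-of-symptoms result to mean. A treatment that shortened symptoms without changing discharge decisions would show no effect on that result. A treatment that changed only discharge decisions would show one.

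**Working it through.** The plan states no figure here to reproduce. The check is a comparison of texts plus a count of scheduled assessments.

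**1. What the duration variable contains.** It starts at first dose and ends at an investigator's readiness judgement (SAP 5.3.1.3). No sign or symptom has to be absent for the event to occur. Item 15 lies outside clinician items 1 to 14, which SAP 5.4.1 and Attachment 4 score for severity.

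**2. Whether another variable fills the gap.**
- Time to clinical stability (SAP 5.3.1.3) combines oxygen supplementation, feeding/hydration support, respiratory rate and heart rate. It does not use cough, wheeze, retractions, nasal secretions, activity or sleep.
- The return to pre-RSV level variables cover respiratory rate, heart rate and body temperature.
- The functional-status term in SAP 5.3.2.3 has no definition in 5.3.1.
- The PRESORS improvement scores (SAP 5.4.1) count items that fell by at least 2 points, per time point. They are not times to an event.

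No time-to-resolution variable is built from PRESORS items.

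**3. Data collected after discharge.** Discharge is allowed after Day 2 procedures. After that, the caregiver diary runs twice daily to the Day 14 visit and once daily to Day 28, and the clinician form is completed at four visits (post-discharge Time and Events Schedule; Protocol 9.1.1). Ignoring visit windows:

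- Discharge right after Day 2: Days 3 to 14 give 12 × 2 = 24 entries, Days 15 to 28 give 14 × 1 = 14, and 24 + 14 = **38** caregiver entries.
- Discharge on Day 3: the discharge-day entry is made before leaving hospital (in-hospital schedule, footnote h). At most one Day 3 entry then follows discharge, so 1 + (11 × 2) + 14 = **37** at most.
- Clinician assessments in either case: Days 7, 10, 14 and 28 = **4**.

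For a child who has met readiness by discharge, none of these enters the duration variable.

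**4. Illustration.** Take a child judged ready on Day 3, still coughing and wheezing at the Day 10 visit and clear from the Day 14 visit. The SAP records 3 − 1 = 2 days. An interval-censored symptom duration would lie between 10 − 1 = 9 and 14 − 1 = 13 days. The schedule permits this case. The documents do not say how common it is.

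**The case against.** Four points can be made for the SAP.

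- **Symptoms after discharge are analysed.** SAP 5.4.2 summarises clinician and caregiver scores by arm at each scheduled time point, with graphs, and tabulates every item at baseline and Days 7, 14 and 28. This stands. A reader might infer that the symptom objective cannot be answered at all, or that a real effect on symptoms would be invisible in the report. The documents do not support that: faster clearing of cough or wheeze could appear in those summaries.
- **The protocol promises only descriptive PRESORS results.** Protocol 11.3 says the scores will be summarised and compared, and SAP 5.4.1 says the instrument is still being evaluated. This supports labelling the result descriptive. It does not remove the need for a definition, because a descriptive duration also needs an event.
- **Readiness is a PRESORS item based on clinical status.** That is correct, and being asked only in hospital is not a fault in itself, since readiness normally precedes discharge. The fault is that readiness is not symptom resolution and the protocol treats the two as separate endpoints.
- **A simple rule that every item equals 0 would fail.** This stands too. In SAP Attachment 4, caregiver item 1 scores 0 only for excellent general condition, so a recovered child rated good would never resolve. Children with comorbidities, limited to 20% of enrolment with an exception for some aged 24 to 36 months, may have chronic signs.

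A reader might also take 2 days against as many as 13 as the typical error. It is a constructed case, and the documents give no rate of residual symptoms at readiness.

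**Conclusion.** The concern holds for duration only. SAP 5.4.2 reports a discharge judgement under the symptom-duration heading. The duration half of the clinician secondary endpoint, the caregiver exploratory duration endpoint and the viral-load-quartile analysis of duration therefore contain no symptom resolution. About 38 caregiver entries (at most 37 for a Day 3 discharge) and 4 clinician assessments per early-discharged child go unused for this purpose. For the clinician-rated secondary endpoint, the relevant count is the 4.

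The conclusion rests on the text of the SAP and on the scheduled assessments. It assumes that no duration derivation exists in another plan. Neither the primary endpoint nor its error control is affected. The change should be made, but it is not critical to the trial's main conclusion.

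**What to change.** In SAP 5.4.2, replace the pointer with time from first dose to sustained resolution of the scored PRESORS sign and symptom items, using SAP Attachment 4 numbering:

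- **Clinician version:** items 1 to 5, with items 6 to 12 as a second version. Leave out global items 13 and 14.
- **Caregiver version:** items 2 to 12. Leave out global item 1.
- **Threshold:** prespecify before unblinding, as score 0 or, for children with chronic signs, return to pre-RSV status. The clinician form records no pre-RSV level, so the rule must name its source for those children.
- **Scoring:** first reconcile the caregiver scoring in SAP Attachment 4 with the diary in Protocol Attachment 5. For example, the SAP scores skin drawn in between the ribs, while the diary asks whether the ribs are more visible than usual.
- **Censoring:** treat the time as interval-censored, as SAP 5.3.1.1 and 5.3.2.1 already do for time to virus undetectable.
- **Undefined term:** define "Time to return to pre-RSV functional status" from the caregiver item on return to pre-RSV health, or remove it.
- **Use:** put the new variables into the viral-load relationship analyses, and keep readiness for discharge as its own endpoint.

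The cost is SAP text, derivations and the scoring reconciliation, with no new data. The drawbacks are coarse intervals after discharge (clinician at Days 7, 10, 14 and 28; the pre-RSV health item only at discharge, Day 7, Day 14 and the final assessment), some censoring at Day 28, and an instrument not yet fully validated. The result should therefore be labelled descriptive.

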6. SAFETY

All safety analyses will be done on the Safety Set.

6.1. Adverse Events

6.1.1. Definitions

Coding of AE

The verbatim terms used in the eCRF by investigators to identify AEs will be coded using the Medical Dictionary for Regulatory Activities. Events are looked at on the level of their preferred term.

Emergent Adverse Event

Emergent AEs are AEs with onset after first study medication intake or that are a consequence of a pre-existing condition that has worsened since baseline. All reported emergent AEs will be included in the analysis. For each AE, the percentage of subjects who experience at least 1 occurrence of the given event will be summarized by treatment group.

Phase allocation of AE

Adverse events present in the SDTM database are allocated to phases based on their start date. If the start date of an event falls between (or on) the start and stop date of a phase, the AE is attributed to that phase (emergent principle).

Incomplete dates (i.e. time and/or day and/or month and/or year missing):

- In case of partial start or stop dates, the events are allocated to the phases using the available partial information on start and end date; no imputation will be done. If, for instance, for the AE start date only month and year are available, these data are compared to the month and year information of the phases. This rule may lead to multiplication of the event as a consequence of its assignment to multiple phases.
- In case of a completely missing start date, the event is allocated to the first active treatment phase, except if the end date of the AE falls before the start of the first active treatment phase.
- In case of a completely missing end date, the following decision rules apply:
 - in case the date is identified as unknown the date will remain missing;
 - in case the date is not flagged as unknown the date is imputed by the cut-off date of the analysis for subjects still ongoing in the study, and by the end date of the last phase for subjects who discontinue.

Examples:

Screening phase: start date: 02JAN2017 - stop date: 28JAN2017

Treatment phase: start date: 29JAN2017 - stop date: 12AUG2017

1) Adverse event: start date: JAN2017- stop date: 15JUL2017

As the start date only has information about month and year, only this information will be used from the phases and therefore the AE will be assigned to the screening phase as well as to the treatment phase.

2) Adverse event: start date: JAN2017- stop date 27JAN2017 As the AE stops before or at the start of the treatment phase, it is only assigned to the Screening phase.

Remarks:

In addition to the date information, time information is taken into account to allocate AEs to phases.

